7.9.2.1.5 Determination of Subjects' Data for Analysis

ITT population with data available will be used for the primary analysis on primary endpoint. For the secondary analysis, PP population will be used on the primary endpoint.

7.9.2.1.6 Missing Data Analysis

No statistical techniques will be used to impute missing data considering that time-to-event analysis will appropriately account for censoring.

7.9.2.2 Secondary Endpoints

The following are the analysis methods for the secondary endpoints in the VLU single-arm study. There are no formal hypothesis tests for any of these endpoints.

7.9.2.3 Effectiveness secondary endpoints

The following ulcer-specific effectiveness endpoints will be evaluated:

1. Ulcer healing rate

Endpoint Definition

Ulcer healing rate is calculated by the percentage of the ulcer area healed, which is

$$100 * (1 - \text{Area}_k / \text{Area}_0)$$

for subject visit k . Area_0 indicates the wound area at baseline in cm^2 . Measurements are taken by an independent core laboratory through 24 months or until ulcer healing has been confirmed. When the ulcer healing is confirmed, the ulcer healing percentage shall be set to 100. If Area_k is larger than Area_0 , then the percentage is set to 0.

Analysis Methods

Mean, standard deviation and sample size will be presented on Ulcer healing rate. Summary statistics will also be provided for area at baseline and area at each subject visit k .

Determination of Subjects for Analysis

ITT population with data available will be used.

2. Ulcer recurrence on the target limb through 60 months.

Endpoint Definition

Sites document the occurrence of an ulcer recurrence at subject visits along with the date of the recurrence.

Analysis Methods

The Kaplan-Meier estimates through 60 months on the time to ulcer recurrence will be provided. The subjects who are lost to follow up or exit without recurrence will be censored at the time of last contact. Day 0 is the day of ulcer healing.

Determination of Subjects for Analysis

Subjects from the ITT population with healed ulcers

3. Ulcer-free time

Endpoint Definition

Days between initial ulcer healing and first ulcer recurrence, as applicable, through 60 months.

Analysis Methods

Summary statistics including mean, standard deviation, median, minimum and maximum will be provided.

Determination of Subjects for Analysis

Subjects who have experienced a healed ulcer followed by an ulcer recurrence.

The following generic effectiveness endpoints will be evaluated:

4. Anatomic closure of the primary target vein at 30 days, and 12, 24, 36, 48 and 60 months:

Endpoint Definition

For subjects treated with the VenaSeal™ system it is defined as DUS showing vein closure, for the primary target vein, along the entire treated vein segment with no discrete segments of patency exceeding 5 cm.

Analysis Methods

The probability of primary target vein closure of any primary target vein at each time point will be summarized. The probability will be estimated using the Kaplan-Meier method. Day zero is the date of the index procedure. The censoring time is the time to last study visit (scheduled or unscheduled), the time point for analysis, or time to exit, whichever comes first. Lack of anatomic closure on the date of the

index procedure will not be considered relevant to this endpoint, since some treatments may not achieve closure immediately.

Determination of Subjects for Analysis

ITT population

5. Anatomic closure of target vein at 30 days, and 6, 12, 24, 36, 48 and 60 months:

Endpoint Definition

Anatomic closure of the target vein is defined as DUS showing target vein closure along the entire treated vein segment with no discrete segments of patency exceeding 5 cm.

Analysis Methods

The probability of target vein closures of any target vein at each time point will be summarized. The probability will be estimated using the Kaplan-Meier method. Day zero is the date of the index procedure. The censoring time is the time to last study visit (scheduled or unscheduled), the time point for analysis, or time to exit, whichever comes first. Lack of anatomic closure on the date of the index procedure will not be considered relevant to this endpoint because some treatments may not achieve closure immediately.

Determination of Subjects for Analysis

ITT population

6. Technical success of each target vein immediately post-index procedure

Endpoint Definition

Technical success of the target vein is defined as DUS taken immediately post-index procedure showing target vein closure along the entire treated vein segment with no discrete segments of patency exceeding 5 cm.

Analysis Methods

The percentage of technical successes will be summarized by treatment arm in each study. The numerator is the number of technical successes, the denominator is the number of target veins treated at the index procedure.

Determination of Subjects for Analysis

AT population

7. Reintervention of any target vein (including primary target vein) through 60 months.

Endpoint Definition

A reintervention is a retreatment of any segment of any target vein in the target limb previously treated as part of the study at the index procedure. Reinterventions are assessed at each follow-up visit.

Analysis Methods

The rate of reintervention will be summarized. The rate is calculated such that the numerator is the number of reinterventions and the denominator is the number of vein-years of follow-up. The amount of follow-up per person is defined as their date of exit or last known follow-up minus their date of index procedure. The vein-years is the amount of person-years times the number of target veins.

Determination of Subjects for Analysis

ITT population

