10.17. Subject Exit, Withdrawal or Discontinuation

10.17.1. Study Exit

A study exit CRF is required for all subjects. Prior to exiting a subject from the study, it is recommended to follow the subject until all ongoing system and/or procedure related AEs are resolved or unresolved with no further actions planned. Following exit, subjects will continue to receive standard medical care. Upon exiting from the study, no further study data will be collected, or study visits will occur for the subject. All data available through the time of the subject's exit will be used for analysis.

Subjects are urged to remain in the study as long as possible but may be exited from the study for any of the following situations:

- Study completed
- Subject lost to follow-up
- Subject death
- Screen Failure
- Subject didn't receive treatment for any of the target vein
- Subject chooses to withdraw (e.g., consent withdrawal, relocation to another geographic location)
- Investigator deems withdrawal necessary (e.g., medically justified, failure of subject to maintain adequate study compliance).

The following information is required to be collected at study exit:

- Date of the exit
- Reason for exit.

If discontinuation is because of safety, the subject may be asked to be followed for collecting safety data outside the clinical investigation.

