Sclerotherapy	Non-surgical procedure where an irritant (i.e. sclerosant) is directly injected into the vein, leading to irreversible endothelial injury and causing the vein to spasm and collapse.
Screen Failure	Subjects who signed and dated the Informed Consent Form, but who no longer meet all eligibility criteria before the point of enrollment.
Screened	Subjects who meet all eligibility criteria will be considered screened from the moment they have signed and dated the ICF
Successful treatment	Completion of the assigned treatment including any reattempt to complete the index procedure.
Target limb	Target limb is the limb identified to be treated limb in the study. In case of bilateral disease with both limbs meeting study eligibility criteria, the treating physician designating the more severe limb depending on the higher CEAP score or most symptomatic according to the patient will be the target limb.
Target Vein (s)	Any additional superficial truncal vein (s) in the target limb beyond the primary target vein which will be treated after the PTV during the index procedure.
Treatment zone	Broad and linear area surrounding the target vein and access site.

Medtronic Business Restricted

CONFIDENTIAL

VENASEAL SPECTRUM Clinical Investigation Plan

MDT18034

Version 5.0

Page 151 of 164

Medtronic

Thrombophlebitis migrans	Advancing or migratory thrombophlebitis that involves multiple vessels at the same time.
Thrombus extension: a. Endothermal Heat Induced Thrombus extension (EHIT) b. Endothermal Glue Induced Extension (EGIT)	Extensions of a thrombus that extend from the treated vein (GSV, SSV, ASV) into the deep venous system. Three different types of extension with VenaSeal to be distinguished: 
1. A pure glue extension – this looks like a very thin line and is rigid, and is detected immediately after the procedure.2. A glue/thrombus combination: This glue/thrombus combination is detected immediately after the procedure like pure glue extension.3. Thrombus extensions: This could be detected at all intervals/follow up periods after the procedure.
Ulcer healing rate	Percent of the ulcer area healed and calculated per given time period on the target limb. The percent healed is determined by an independent core laboratory.
Ulcer recurrence	First occurrence of ulcer re-appearance after it has healed.
Ulcer-free time	Calculated as time between ulcer healing and first instance of ulcer recurrence.

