7.4 Handling of Missing, Unused, and Spurious Data and Dropouts

Every effort will be undertaken to minimize missing data. A combination of sensitivity analysis and multiple imputation of the primary endpoints will be performed to assess the potential impact of missing data. The details will be described in the section 7.9.1.1.6 Missing Data Analysis below.

Unless otherwise specified, no statistical techniques will be used to impute missing data for the other objectives. The number of subjects included in each analysis will be reported. In time-to-event outcomes drop-outs will be censored at the time of discontinuation, consistent with the Kaplan-Meier approach.

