7.9.2 VLU (Single Arm) Study

Analyses will be performed on all ITT subjects in the VLU Study.

Descriptive statistics will be presented for the study endpoints. For categorical variables, the count and percentage of subjects with each outcome will be presented. For continuous variables, summary statistics (mean, standard deviation, median) will be presented. Time to-event response variables may be displayed by using a Kaplan-Meier plot or cumulative incidence curve.

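### The Kaplan-Meier estimate of ulcer recurrence censors deaths, so it describes recurrence as if no one died; the proportion of healed subjects who actually recur should be reported beside it

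*SAP*

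**What the plan says.** SAP 7.9.2.3 item 2 sets the estimator, time origin, analysis set and censoring rule for ulcer recurrence in the single-arm VLU Study:

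- Estimator: "The Kaplan-Meier estimates through 60 months on the time to ulcer recurrence will be provided".
- Time origin: "Day 0 is the day of ulcer healing".
- Analysis set: "Subjects from the ITT population with healed ulcers".
- Censoring: "The subjects who are lost to follow up or exit without recurrence will be censored at the time of last contact".

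Item 2 does not mention death. Protocol 10.17.1 (Study Exit) does: "Subject death" is one of the listed exit situations, next to loss to follow-up and withdrawal. The general rule in SAP 7.4 makes no separate provision for death either: "In time-to-event outcomes drop-outs will be censored at the time of discontinuation, consistent with the Kaplan-Meier approach".

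Protocol Appendix B defines recurrence as "First occurrence of ulcer re-appearance after it has healed", an event that a subject who has died can no longer have.

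The introduction to SAP 7.9.2 adds a general remark on presentation: "Time to-event response variables may be displayed by using a Kaplan-Meier plot or cumulative incidence curve". Neither document names a competing event or a competing-risk estimator for this endpoint.

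**The concern.** Censoring assumes that the subject could still have the event later, unobserved. That is reasonable for someone lost to follow-up. It does not describe someone who has died. Kaplan-Meier in effect redistributes each dead subject's weight to those still at risk, so its complement answers how often ulcers would recur if no one died. A reader of a single-arm report is likely to take a 60-month recurrence figure as the share of healed subjects whose ulcer came back. These are different quantities, and the SAP does not say which it intends.

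Recurrence is a named secondary objective of the VLU Study (protocol 5.1.2). With no comparator the figure can only be read as an absolute probability, so its meaning should be stated. Follow-up is long enough for deaths to occur. The only exclusion tied to survival is life expectancy under one year, given as an example within an investigator-judgement criterion (protocol 9.6, criterion 6), and it does not address deaths in later years.

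**Working it through.** **Does the SAP's mention of a cumulative incidence curve settle it?** No. The remark in 7.9.2 is optional, concerns display and defines no competing event. Elsewhere the SAP pairs a cumulative incidence figure with a Kaplan-Meier estimator (7.9.1.2.4, 7.9.1.7, 7.9.2.6), so the phrase does not signal a competing-risk method. The endpoint-specific text in 7.9.2.3 governs.

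**Direction.** Both estimators add up, over recurrence times, the recurrences divided by the number at risk, multiplied by a survival term. In one minus Kaplan-Meier that term ignores deaths. In Aalen-Johansen it falls at deaths as well, so it is never larger. Hence one minus Kaplan-Meier is never below Aalen-Johansen.

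**Size.** The plan gives no recurrence probability, mortality or sample size for this endpoint, so there is no figure to reproduce and the rates below are assumptions. Let R be net recurrence at 5 years and m annual mortality, with constant hazards:

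- recurrence hazard a = -ln(1 - R)/5; death hazard b = -ln(1 - m)
- one minus Kaplan-Meier at 5 years = R
- cumulative incidence at 5 years = a/(a + b) × [1 - exp(-5(a + b))]

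Example, R = 40% and m = 3%: a = 0.1022, b = 0.0305, a + b = 0.1326. Cumulative incidence = 0.7703 × (1 - 0.5152) = 37.3%. Excess = 40.0 - 37.3 = 2.7 points.

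Excess of one minus Kaplan-Meier over cumulative incidence, in percentage points:

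| Net recurrence at 5 years | m = 1% | 2% | 3% | 5% | 8% | 10% |
|---|---|---|---|---|---|---|
| 20% | 0.5 | 0.9 | 1.4 | 2.3 | 3.5 | 4.3 |
| 30% | 0.7 | 1.4 | 2.0 | 3.3 | 5.2 | 6.3 |
| 40% | 0.9 | 1.8 | 2.7 | 4.3 | 6.7 | 8.2 |
| 50% | 1.1 | 2.2 | 3.2 | 5.2 | 8.1 | 10.0 |
| 60% | 1.3 | 2.5 | 3.7 | 6.1 | 9.4 | 11.5 |

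The upper end of the range comes from recurrence of 20% a year with m = 10%. There R = 1 - 0.8^5 = 67.2%, a = 0.2231, b = 0.1054, and cumulative incidence = 0.6793 × (1 - 0.1935) = 54.8%, an excess of about 12 points. With m = 0 the excess is zero.

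**Simulation check.** 100 healed subjects, 10% lost to follow-up over 5 years, 3,000 runs per scenario. Mean one minus Kaplan-Meier against mean Aalen-Johansen:

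- R = 30%, m = 3%: 29.9% against 27.9%
- R = 40%, m = 5%: 40.1% against 35.8%
- R = 50%, m = 5%: 50.0% against 44.8%
- R = 40%, no deaths: 40.0% for both

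One minus Kaplan-Meier was at or above Aalen-Johansen in every run.

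**Horizon.** Time runs from healing, but follow-up ends at the 60-month visit counted from the procedure (target day 1825, protocol 10.2, Table 8). At the planning median of 70 days to healing (SAP 6.2.1), a subject seen on the target day has 1825 - 70 = 1755 days after healing, short of 60 months. A subject who heals at 12 months (day 365) has 1825 - 365 = 1460 days, the protocol's target for 48 months. So few subjects can be observed for a full 60 months after healing, while 48 months is within reach for anyone who heals in the first year and stays in follow-up.

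**The case against.** The strongest reply is that this is a choice of estimand and not an error. Item 2 promises Kaplan-Meier estimates of time to recurrence and does not claim to give the share of all healed subjects who recur. Net recurrence is a legitimate target, and it is the quantity needed by anyone who wishes to apply mortality separately. This stands: the estimate is too high only if read as the actual proportion.

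Three stronger readings are tempting, and the documents do not support them:

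- A reader might infer that the method understates how durable healing is. Cumulative incidence is lower because subjects die before they can recur, not because healing lasts longer. For durability, the net estimate is arguably the closer one.
- A reader might infer that a cost-effectiveness model will be misled. SAP 7.11 leaves that work to the health economics team and a separate plan, and nothing says that this curve enters a model as a crude probability.
- A reader might infer that the excess must be material. The documents give no mortality. The upper end of the range needs 10% deaths a year, which is 1 - 0.9^5 = 41% dead by five years, together with recurrence of 20% a year.

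Sampling error also matters. With 100 healed subjects (an assumption; enrolment is up to 125) and 40% recurring, the binomial standard error is √(0.4 × 0.6/100) = 4.9 points, a 95% half-width of 1.96 × 4.9 = 9.6 points. A shift of 1-3 points would not change a descriptive reading. Finally, deaths are not hidden, since SAP 7.10 lists them all with reasons. That listing does not give the recurrence proportion, however.

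**Conclusion.** The point holds in a limited form. Taken together, SAP 7.9.2.3 item 2 and protocol 10.17.1 censor recurrence-free deaths; this is inferred from the two texts, because item 2 does not name death. The planned figure is therefore net recurrence, it is not labelled as such, and it cannot be read as the proportion of healed subjects who recur. The difference is always in the same direction. Over the assumed range it is about 0.5 to 12 percentage points, and where in that range the study will fall cannot be told from the documents. It rests on constant hazards over a full five years after healing, which most subjects will not have.

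The endpoint is descriptive, with no hypothesis test (SAP 7.9.2.2). No error rate, sample size or primary result is touched. This is a worthwhile clarification and not a flaw that threatens a conclusion.

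**What to change.** In SAP 7.9.2.3 item 2:

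- Report the cumulative incidence of first recurrence from the day of healing, with death as a competing event (Aalen-Johansen; the EVENTCODE option of PROC LIFETEST in SAS).
- Give 95% confidence intervals at 12, 24, 36 and 48 months after healing, and later only where enough subjects remain at risk.
- Report the number of recurrence-free deaths.
- Keep loss to follow-up and withdrawal as censoring.
- Keep the Kaplan-Meier estimate, labelled as the net (death-censored) estimate.

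The cost is a few SAP sentences and a software option. Dates of death are already collected (protocol 12.9), so no new data or visits are needed. The small downside is a second curve to explain in the report.

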5.1.2. Secondary Objectives

The key secondary objectives are to compare the VenaSeal™ system to surgical stripping and ETA in achieving the anatomical closure of superficial truncal veins at 6 months, and the ability to return to work post-index procedure.

For all subjects, the secondary objective of the study is to evaluate the VenaSeal™ system in the treatment of symptomatic venous reflux in the superficial truncal veins. Specific areas of analysis include: effectiveness, safety, healthcare utilization, patient experience, and treating physician experience.

In addition, secondary objectives in the VLU Study include ulcer healing rate, ulcer recurrence, and ulcer-free time.

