Provider Experience secondary endpoint

19. Provider experience will be assessed post-index procedure, evaluating overall satisfaction with the procedure.

VLU Study:

The primary endpoint of the VLU Study is referenced in section 5.2.1, Primary endpoints.

The following ulcer-specific effectiveness endpoints will be evaluated:

20. Ulcer healing rate, as measured by the percentage of the ulcer area healed per given time period, according to an independent core laboratory through 24 months or until ulcer healing has been confirmed.
21. Ulcer recurrence on the target limb, assessed at all follow-up timepoints following ulcer healing through 60 months.
22. Ulcer-free time, calculated as days between initial ulcer healing and first ulcer recurrence, as applicable, through 60 months.

In addition, the primary endpoints and any other applicable endpoints of the Randomized Studies will be also assessed for the VLU Study:

23. Peri-procedural patient satisfaction as measured by a validated patient-centered venous treatment satisfaction questionnaire (VenousTSQe) at 30 days.
24. Patient satisfaction as measured by a validated patient-centered venous treatment satisfaction questionnaire (VenousTSQs) at 30 days.
25. Elimination of clinically relevant superficial truncal disease in target vein at the time of index procedure as measured by the percentage of target veins successfully treated.

6. Study Design

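### SAP 7.9.2.3 item 3 summarises ulcer-free time only in subjects whose ulcer recurred, so the reported mean and median run short as a measure of ulcer-free time after healing

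*SAP*

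**What the plan says.** Protocol 5.1.2 lists ulcer-free time as an objective separate from recurrence: "secondary objectives in the VLU Study include ulcer healing rate, ulcer recurrence, and ulcer-free time". Protocol 5.2.3 defines the endpoint: "Ulcer-free time, calculated as days between initial ulcer healing and first ulcer recurrence, as applicable, through 60 months". Appendix B gives the same interval. Neither place says what value a subject without recurrence takes.

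SAP 7.9.2.3 item 3 repeats the definition ("Days between initial ulcer healing and first ulcer recurrence, as applicable, through 60 months") and sets the method: "Summary statistics including mean, standard deviation, median, minimum and maximum will be provided". Its analysis set is "Subjects who have experienced a healed ulcer followed by an ulcer recurrence". No censoring is described.

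Item 2 of the same section, ulcer recurrence, covers the same interval with day 0 at healing. It uses Kaplan-Meier in "Subjects from the ITT population with healed ulcers", and "The subjects who are lost to follow up or exit without recurrence will be censored at the time of last contact". SAP 7.4 states the general rule: "In time-to-event outcomes drop-outs will be censored at the time of discontinuation, consistent with the Kaplan-Meier approach".

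**The concern.** Item 3 selects subjects on the outcome being measured. Whoever heals and does not recur during follow-up, which is the best result, is removed. What remains is time to recurrence given that recurrence was seen before follow-up ended. Late healers have less time left in which a recurrence can be seen, which shortens the figure further.

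Readers will probably take a number headed ulcer-free time as a statement of how long healing lasts. As specified it answers a narrower question and understates durability, most of all when few subjects recur. It would also stand beside item 2's curve, which describes the same interval in a different set of subjects.

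**Working it through.** Neither document states an expected ulcer-free time or recurrence rate, so there is no planned figure to reproduce. The check asks how far the recurrers-only summary lies from the same quantity in all healed subjects.

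**Inputs**
- Time to healing: exponential with median 70 days (SAP 6.2.1, Protocol 14.2.1), so the mean is 70/ln 2 = 101 days.
- End of follow-up: day 1825, the 60-month target in Protocol 10.2, Table 8.
- Recurrence after healing: constant hazard h, with one-year risk of 5, 15 or 30%. This is an assumption, shown as a range. h = −ln(1 − one-year risk)/365.
- No drop-out. This is also an assumption.

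**Step 1: fixed window, checkable by hand.** Give every healed subject the average remaining follow-up, τ = 1825 − 101 = 1724 days.
- Share of healed subjects who recur: p = 1 − exp(−hτ)
- Mean in recurrers (SAP set): 1/h − τ(1 − p)/p
- Median in recurrers (SAP set): −ln(1 − p/2)/h
- Mean ulcer-free time within the window, all healed: p/h
- Underlying median time to recurrence: ln 2/h

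| One-year risk | 1/h (days) | p | Mean, recurrers | Median, recurrers | Mean within window, all healed | Underlying median |
|---|---|---|---|---|---|---|
| 5% | 7116 | 0.215 | 827 | 810 | 1531 | 4932 |
| 15% | 2246 | 0.536 | 753 | 700 | 1204 | 1557 |
| 30% | 1023 | 0.814 | 631 | 535 | 834 | 709 |

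**Step 2: healing times allowed to vary.** Simulating exponential healing with follow-up to day 1825 gives:
- mean in recurrers: about 830 / 754 / 629 days;
- mean within follow-up, all healed: 1531 / 1201 / 832 days;
- share of healed subjects entering the SAP figure: 21 / 54 / 81%.

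The means agree with Step 1 to within 3 days.

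**Step 3: size of the gap.** The recurrers-only mean is shorter by 1531 − 830 = 701, 1201 − 754 = 447 and 832 − 629 = 203 days. The all-healed mean is itself cut off at the end of follow-up, so these gaps do not come from projecting beyond the data.

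**Step 4: response to the recurrence rate.** From 5% to 30% one-year recurrence the recurrers-only mean falls by (830 − 629)/830 = 24%. The all-healed mean falls by (1531 − 832)/1531 = 46%. The recurrers-only median falls by (810 − 535)/810 = 34%. Under a constant hazard the recurrers-only mean cannot exceed half the window, 1724/2 = 862 days, however durable the healing.

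**The case against.** The strongest reply is that the valid analysis is already in the plan. Item 2 estimates time from healing to recurrence in all healed ITT subjects, with censoring, and a median or restricted mean can be read from that curve. This stands: durability information is not lost, and the defect is confined to the figure reported under item 3.

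A second reply is that the SAP reads the protocol literally. The interval has no end date in a subject who never recurs, and the protocol's qualifier about applicability could be read as limiting the endpoint to recurrers. The reading is possible, but nothing in the protocol requires these subjects to be deleted, and item 2 shows that the SAP's usual way of handling an open interval is censoring.

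A third reply is that the consequence is small. The study has one arm, the endpoint is descriptive with no hypothesis test, and SAP 7.4 requires the number of subjects in each analysis to be reported, so the reduced denominator will be visible. This also stands and limits the importance of the point.

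Two stronger readings are tempting and should not be drawn:
- A reader might infer that the figure barely responds to how well healing lasts. In the range above it moves about half as much as the all-healed mean (24% against 46%), and its median moves 34%. It is damped, not inert. It stays flat only under a particular pattern, such as a changing share who never recur with unchanged timing in the rest, and the documents give no basis for assuming one.
- A reader might infer that the figure can move the wrong way. In the range above it falls steadily as recurrence rises. A reversal needs two different recurrence patterns to be compared: 20% recurrence, all early, gives a mean of 183 days, against 678 days for 80% recurrence at constant hazard over five years from healing. The documents describe no such patterns, and the study has no second arm.

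**Conclusion.** The point holds as a defect in one descriptive endpoint. As written, item 3 yields time to recurrence among subjects who recurred, and as a measure of ulcer-free time after healing it is biased short. Under the stated assumptions the mean is short by roughly 200 to 700 days, with the largest gap where recurrence is rarest and only about a fifth of healed subjects contribute.

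That subjects without recurrence are excluded follows from the SAP text alone. The size rests on the assumed constant hazard, the assumed 5 to 30% one-year recurrence and no drop-out. No hypothesis test or sample size is affected, and item 2 remains a sound analysis of the same interval. The change is worth making before the VLU results are reported.

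**What to change.** In SAP 7.9.2.3 item 3:
- change the analysis set to all ITT subjects with a healed ulcer;
- censor subjects without recurrence at last contact, as in item 2;
- report the restricted mean ulcer-free time to a fixed horizon from healing, for example 12 and 36 months, with 95% confidence intervals. Core-laboratory healing verification ends at 24 months, and 60 − 24 = 36, so a subject verified as healed by then still has about 36 months of scheduled follow-up;
- report the Kaplan-Meier median only if it is reached. At 5% one-year recurrence the underlying median is about 4932 days, far beyond day 1825, so it should not be the sole summary.

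If the present summary is kept, label it *time to recurrence among subjects who recurred* and print its denominator beside the number healed.

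The cost is SAP wording and a little programming. The healing, recurrence and last-contact dates are already needed for item 2.
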